## 7. ADVERSE EVENTS MANAGEMENT

### 7.1. Adverse Events

This study is a long-term observational Registry in which no study medication will be administered. Adverse events related to the initial Gilead-sponsored treatment protocol will be followed in accordance with that initial protocol.

As a consequence adverse event reporting in this Registry will be restricted to the following:

- Any adverse event occurring as a consequence of procedures required by this Registry protocol will be followed and documented in accordance with provisions outlined below.

For the purposes of this Registry an AE is any untoward medical occurrence in a clinical study subject associated with procedures mandated by this Registry protocol. An AE can therefore be any unfavorable and unintended sign, symptom, or disease temporally associated with procedures mandated by this Registry (e.g., hematoma following venipuncture).

An AE does not include the following for this Registry:

- Any medical condition or clinically significant laboratory abnormality with an onset date before the consent form is signed is not an AE.
- Any medical condition or clinically significant laboratory abnormality occurring after the consent form is signed and is related to the initial Gilead-sponsored treatment protocol. Any events related to the initial treatment protocol will be followed according to that treatment protocol.

### 7.2. Serious Adverse Events

Any SAEs occurring during the initial Gilead-sponsored treatment protocol will be followed, documented and reported under that treatment protocol. Similarly any new SAEs occurring while the subject is participating in the Registry that are considered to be related to study drugs administered or procedures in the initial Gilead-sponsored treatment protocol will be followed, documented and reported under the initial Gilead-sponsored treatment protocol.

The only SAEs which will be reported under this Registry are events considered to be related to procedures mandated by the Registry protocol.

**Serious adverse event (SAE)** is defined as any adverse event that results in any of the following outcomes:

- Death
- Life-threatening situation (subject is at **immediate** risk of death)

- In-patient hospitalization or prolongation of existing hospitalization (excluding those for study therapy or placement of an indwelling catheter, unless associated with other SAEs)
- Persistent or significant disability/incapacity
- Congenital anomaly/birth defect in the offspring of a subject who received investigational medicinal product. All pregnancy events will be followed to resolution/outcome in the initial Gilead-sponsored treatment protocol
- Other: medically significant events that may not be immediately life-threatening or result in death or hospitalization, but based upon appropriate medical and scientific judgment, may jeopardize the subject or may require medical or surgical intervention to prevent one of the outcomes listed above

### **Clarification of Serious Adverse Events**

- Death is an outcome of an AE, and not an adverse event in itself.
- “Life-threatening” means that the subject was at immediate risk of death from the event as it occurred. This does not include an event that might have led to death if it had occurred with greater severity.
- “In-patient hospitalization” means the subject has been formally admitted to a hospital for medical reasons, for any length of time. This may or may not be overnight. It does not include presentation and care within an emergency department.

The relationship to study procedures (e.g., invasive procedures such as venipuncture) should be assessed using the following considerations:

- **No:** Evidence exists that the AE has an etiology other than the study procedure.
- **Yes:** The AE occurred as a result of protocol-mandated procedures such as venipuncture.

## **7.3. Serious Adverse Event Reporting Requirements**

### **7.3.1. All Serious Adverse Events**

Gilead Sciences may be required to expedite to worldwide regulatory authorities reports of SAEs, Serious Adverse Drug Reactions (SADRs) or Suspected Unexpected Serious Adverse Reactions (SUSARs) in line with relevant legislation, including the applicable US FDA Code of Federal Regulations, the European Commission Clinical Trials Directive (2001/20/EC); therefore, Gilead Sciences (or the CRO on the behalf of Gilead Sciences) must be notified immediately regarding the occurrence of any SAE or SADR that occurs after the subject consents to participate in the Registry, including SAEs/SADRs resulting from protocol-mandated procedures. The procedure for reporting SAEs is as follows:

- All SAEs will be recorded in the eCRF database within 24 hours of the investigator's knowledge.
- Site personnel record all SAE data in the eCRF database and from there transmit the SAE information to Gilead Drug Safety and Public Health (DSPH) within 24 hours of the investigator's knowledge of the event. Detailed instructions for how to record SAE data in the eCRF database can be found in the eCRF completion guidelines.
- If for any reason it is not possible to record the SAE information electronically (i.e. the eCRF database is not functioning) record the SAE on the paper SAE reporting form and submit within 24 hours by emailing or faxing the report form to the attention of Gilead DSPH:

Gilead Sciences                      [contact]  
DSPH:                                      E-mail:        safety\[contact]

- As soon as it is possible to do so, any SAE reported on paper via email or fax must be transcribed into the eCRF database according to instructions in the eCRF completion guidelines.
- If an SAE has been reported via a paper form because the eCRF database has been locked, no further action is necessary.
- For fatal or life-threatening events, also e-mail or fax copies of hospital case reports, autopsy reports, and other documents when requested and applicable. Transmission of such documents should occur with Personal Subject Details de-identified, without losing the traceability of a document to the Subject Identifiers.
- Gilead Sciences may request additional information from the investigator to ensure the timely completion of accurate safety reports.

The investigator must take all therapeutic measures necessary for resolution of the SAE. Any medications necessary for treatment of the SAE must be recorded in the event description section of the SAE form.

Follow-up of SAEs will continue through the last day on the Registry and/or until a conclusive outcome (e.g., resolved, resolved with sequelae, lost to follow-up, fatal) is achieved.

For SAEs related to the previous Gilead-sponsored treatment protocol once the treatment protocols eCRF database has been locked, the SAE should be reported via a paper form specific to the previous Gilead-sponsored treatment protocol. Submit the paper SAE report form within 24 hours by emailing or faxing the report form to the attention of Gilead DSPH:

Gilead Sciences                      [contact]  
DSPH:                                      E-mail:        safety\[contact]

### **7.3.2. Investigator and Sponsor Reporting Requirements for SAEs**

Any SAE deemed by the investigator to be related to a protocol-mandated procedure should be collected and reported throughout the Registry study and reported to Gilead Sciences DSPH using the SAE report form.

An SAE may qualify for reporting to regulatory authorities. All Investigators will receive a safety letter notifying them of relevant SUSAR reports. The Investigator should notify the IRB as soon as is practical, of serious events in writing where this is required by local regulatory authorities, and in accordance with the local institutional policy.

In accordance with the EU Clinical Trials Directive (2001/20/EC), Gilead will notify worldwide regulatory authorities and the relevant Ethics Committees in concerned Member States of applicable SUSARs.

### **7.4. Clinical Laboratory Abnormalities and Other Abnormal Assessments as AEs or Serious AEs**

Laboratory abnormalities are usually not recorded as AEs or SAEs. Laboratory abnormalities will only be recorded as an AE/SAE if they are related to a protocol-mandated procedure and require medical or surgical intervention or discontinuation from the study.

### **7.5. Procedures to be followed in the Event of Pregnancy**

Procedures to be followed in the event of pregnancy occurring on the initial treatment protocol are detailed in the Gilead-sponsored treatment protocol. No additional pregnancy reporting requirements are included in this Registry protocol.

## 8. STATISTICAL CONSIDERATIONS

### 8.1. Analysis Objectives

Treatment regimen is defined as treatment regimen in the initial Gilead-sponsored treatment protocol.

#### 8.1.1. Primary Objective

The primary objective of this study is to assess the long-term safety of anti-HCV regimens in the pediatric population as determined by assessment of growth and development.

#### 8.1.2. Secondary Objectives

The secondary objectives of this study are:

- To determine whether subsequent detection of HCV RNA in subjects who relapse following sustained virologic response (SVR) represents the re-emergence of pre-existing virus, the development of resistance mutations, or whether it is due to re-infection;
- To characterize resistance mutations and the persistence of resistance mutations in pediatric subjects who did not achieve SVR;

#### 8.1.3. Exploratory Objective

PPD

### 8.2. Primary Safety Endpoints

The primary safety endpoints are:

- Growth data by visit grouped by age and gender;
- Development by Tanner Pubertal Stage Assessment;

### 8.3. Other Endpoints of Interest

PPD

- 
- 
- 
- 
- 

## **8.4. Methods of Analysis**

All individual data will be listed as measured. All statistical summaries and analyses will be performed using SAS® software (SAS Institute, Cary, North Carolina, USA).

### **8.4.1. Analysis Sets**

#### **8.4.1.1. Safety Analysis Set**

The safety analysis set is defined as all enrolled subjects.

#### **8.4.1.2. Efficacy Analysis Set**

Efficacy Analysis Set is the same as safety analysis set.

### **8.4.2. Data Handling Conventions**

Missing data can have an impact upon the interpretation of the trial data. In general, values for missing data will not be imputed.

All available data for subjects who do not complete the study will be included in data listings.

HCV RNA values below the LLoQ for the assay will be set to the lower limit minus 1 for calculation of summary statistics for the actual HCV RNA values and the change from baseline values by study visit. The reported values will be provided in the HCV RNA listing.

For selected analyses, HCV RNA data (IU/mL) will be transformed to the logarithmic (base 10) scale ( $\log_{10}$  IU/mL).

### **8.4.3. Interim Analyses**

Interim analyses may be performed on an ad hoc basis, approximately every year throughout the duration of the Registry. All endpoints will be summarized by visit.

## **8.5. Demographic Data and Enrollment Characteristics**

Demographic and enrollment measurements will be summarized using standard descriptive methods.

Demographic summaries will include gender, race (with Asian-Oriental, Asian-Indian, Asian-Other combined to Asian), ethnicity (Hispanic or non-Hispanic), and age.

Enrollment data will include a summary of HCV RNA levels, HCV genotype and IL28B genotype, Tanner Pubertal Stage Assessment, and growth data.

## **8.6. Safety Analyses**

Analysis of safety measures will be descriptive and will include subjects in the Safety analysis set. All safety data collected on or after the date of enrollment through the end of the study will be summarized.

### **8.6.1. Extent of Exposure**

This is a Registry study with no active treatment; hence, extent of exposure to study drug is not applicable.

### **8.6.2. Adverse Events**

Clinical adverse events will be coded using the Medical Dictionary for Regulatory Activities (MedDRA). System Organ Class (SOC), High-Level Group Term (HLGT), High-Level Term (HLT), Preferred Term (PT), and Lower-Level Term (LLT) will be attached to the clinical database.

Events will be summarized on the basis of the data of onset for the event. An adverse event is defined as an event that begins or worsens on or after the date the ICF is signed through study completion or study discontinuation and is classified as related to a study procedure.

Summaries (number and percent of subjects) of adverse events and serious adverse events will be provided.

Data listings will be provided for subjects who discontinued the study due to an adverse event.

### **8.6.3. Other Safety Evaluations**

#### **8.6.3.1. Tanner Pubertal Stage Assessment**

Tanner Stages ([Appendix 3](#)) will be summarized by baseline Tanner Stage using descriptive statistics.

#### **8.6.3.2. Growth Data**

For each subject, body height, body weight, and Z-scores at baseline and at each visit will be calculated based on sex and age.

The changes in body height and weight measurements for all subjects will be examined to determine, for example, if the majority of subjects increased, decreased or stayed the same at each visit. The baseline measurements will be examined to show where the subjects were before the study, in terms of their height and weight, compared to the population. Summary statistics will be calculated for the measurements and the changes in measurements at each visit by sex and overall. Depending on the distribution of the data, either a Wilcoxon signed rank test, or a one-sample t-test will be done to evaluate if the mean or median change from baseline is different from zero.

The number of subjects whose change increases, decreases, and stays the same will be tabulated at each visit. Due to the precise nature of the calculations, the “stays the same” category may be broadened to include changes other than zero, which are negligible (i.e. 0.5).

Z-scores for body weight and height and change from baseline in Z-scores for body weight and height will be summarized by visit. Figures for the median and IQR in height and weight Z-score by visit will be displayed.

In addition, summary statistics of the absolute value and change from baseline in both height and weight will be tabulated by visit.

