	

• History of clinically-significant illness or any other major medical disorder that may interfere with the subject follow-up, assessments or compliance with the protocol.

Study Procedures/ Frequency:	
The subject and/or the subject's parent or legal guardian must provide written consent within 168 days from the last visit of the previous Gilead-sponsored treatment protocol.
 
Subjects will be assessed at Day1 and at Week 24, 48, 72, 96, 144, 192, and 240. At each visit blood will be collected for HCV RNA and viral sequencing (archive), and a quality-of-life survey will be completed. Symptom-directed physical exams, body height and weight measurements, and Tanner Pubertal Stage Assessment (if applicable) will be performed.
 
Only AEs and SAEs considered to be related to study procedures mandated by the Registry protocol will be reported under this Registry. Any treatment related SAEs will be reported within the previous Gilead-sponsored treatment protocol.

---

Test Product, Dose, and Mode of Administration:	No test product will be administered in this Registry.
--	--

---

Reference Therapy, Dose, and Mode of Administration:	None.
---	-------

---

Criteria for Evaluation:	None. This is an observational Registry.
---------------------------------	--

---

Statistical Methods:	Data from this Registry study will be summarized descriptively. Statistical hypothesis testing will not be conducted. All continuous variables will be summarized using an 8-number descriptive summary (n, mean, standard deviation, and median, Q1, Q3, minimum, maximum) by visit. All categorical variables will be summarized by number and percentage of subjects in each categorical definition.
-----------------------------	---

---

This study will be conducted in accordance with the guidelines of Good Clinical Practices (GCPs) including archiving of essential documents.

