#### **3.2. Visit Schedule**

Once enrolled, subjects will be followed for up to 5 years. The subject and/or the subject's parent or legal guardian must provide written consent within 168 days from the last visit of the previous Gilead-sponsored treatment protocol. The Day 1 visit will be documented as the last visit of the previous Gilead-sponsored treatment protocol. Subsequent study visits will occur at Weeks 24, 48, 72, 96, 144, 192, and 240. At each subsequent visit, subjects will have blood drawn for plasma HCV RNA quantification and viral sequencing (archive). In addition, a symptom-directed physical examination, body height and weight measurements, and Tanner Pubertal Stage Assessment (when appropriate) will be performed. A quality-of-life survey will be completed. Reminder phone calls to subjects will be conducted by the site staff at 1-2 months prior to each study visit following the subject's Day 1 visit date.

While participating in the Registry, if a subject tests positive for HCV RNA after non-detectable levels at Day 1 (defined as HCV RNA  $\geq$  LLoQ) or any time throughout the study, they will be asked to return to the clinic for collection of a repeat blood sample for HCV RNA quantitation.

The assessments to be performed at each visit are described in Section 6.

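### The protocol orders a significance test of growth change, with no visit, measure or scale named, although its synopsis rules out hypothesis testing and Section 8.6 calls safety analyses descriptive

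*Protocol*

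**What the plan says.** **Endpoint.** Section 8.2 of the Protocol lists growth as a primary safety endpoint and defines it only as "Growth data by visit grouped by age and gender". No visit or measure is singled out. Section 3.2 gives seven post-baseline visits: "Subsequent study visits will occur at Weeks 24, 48, 72, 96, 144, 192, and 240".

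**Analysis.** Section 8.6.3.2 derives both raw values and Z-scores: "For each subject, body height, body weight, and Z-scores at baseline and at each visit will be calculated based on sex and age". Its paragraph on height and weight measurements says "Summary statistics will be calculated for the measurements and the changes in measurements at each visit by sex and overall". The next sentence orders either a Wilcoxon signed rank test or a one-sample t-test, chosen by the distribution of the data, to "evaluate if the mean or median change from baseline is different from zero". A later paragraph has Z-scores and their changes summarised by visit. It mentions no sex split and no test.

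**Status of testing.** The synopsis, under Statistical Methods, says "Statistical hypothesis testing will not be conducted". Section 8.6 says "Analysis of safety measures will be descriptive and will include subjects in the Safety analysis set".

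**Interim summaries.** Section 8.4.3 allows ad hoc interim analyses about once a year and says "All endpoints will be summarized by visit".

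**The concern.** The synopsis and Section 8.6.3.2 cannot both be followed. One excludes hypothesis tests and the other orders one on a primary safety endpoint. An analyst must choose between them, and two analysts could choose differently.

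If the test is run, the text does not say on what. One test per measure, 14 tests (each measure at each visit) and 42 tests (also in males and in females) could each be defended as the plan. The scale is open as well, and it decides what a significant result means. Growing children gain height and weight, so zero raw change is not a plausible null and rejecting it shows only that they grew. Zero is a meaningful null for Z-score change, and there repeated unadjusted testing produces chance findings.

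The Registry exists because of concern about growth under earlier hepatitis C treatments (Sections 1.1 and 1.2). An unlabelled p-value at a single visit could be read as evidence of harm. An unlabelled non-significant one could be read as evidence of safety.

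**Working it through.** The Protocol states no alpha, sample size or error rate for growth, so there is no figure of its own to reproduce.

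**Step 1. The passages side by side**

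| Place | Position on testing |
|---|---|
| Synopsis, Statistical Methods | No hypothesis tests |
| Section 8.6 | Safety analysis is descriptive |
| Section 8.6.3.2 | A signed rank or one-sample t-test of change against zero will be done |

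The third row contradicts the first and does not fit the second.

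**Step 2. How many tests the text could mean**

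- One per measure: 2.
- Each measure at each visit, all subjects: 2 × 7 = 14.
- The same, also in males and in females: 2 × 7 × 3 = 42.

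The words about visit and sex stand in the summary-statistics sentence, not in the test sentence. Testing by visit is the natural reading, because change from baseline exists only at a visit and the sentences on either side are by visit. Testing by sex is a further inference.

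**Step 3. Bounds if tests were independent**

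Assume two-sided 5% per test, with every null true on the Z-score scale. The chance of at least one false positive is 1 − 0.95^k.

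- k = 2: 1 − 0.95² = 0.0975
- k = 14: 1 − 0.95¹⁴ = 0.512
- k = 42: 1 − 0.95⁴² = 0.884. This is not attainable, because the overall statistic is built from the two sexes. With everything else independent, simulation gives about 0.82.

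**Step 4. Correlated tests**

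Multivariate normal test statistics were simulated for seven visits and two measures in each sex. The sexes were independent and of equal size, with overall = (male + female)/√2. The correlation between height and weight was 0.5, and one common between-visit correlation was varied. The documents give none of these values, so all are assumptions.

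| Between-visit correlation | 14 overall tests, any \|z\| > 1.96 | 42 tests, any \|z\| > 1.96 | 42 tests, any z < −1.96 (false deficit) |
|---|---|---|---|
| 0.3 | 0.445 | 0.745 | 0.446 |
| 0.5 | 0.384 | 0.676 | 0.383 |
| 0.7 | 0.306 | 0.557 | 0.304 |
| 0.9 | 0.197 | 0.397 | 0.208 |

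Moving the height–weight correlation between 0 and 0.7 changes little. At between-visit correlation 0.5, the 42-test figure runs from 0.70 to 0.64. At 0.9 it runs from 0.43 to 0.37.

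**Step 5. Scale**

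These rates apply only to Z-score change. If raw change is tested, the null is false by design and a false-positive rate has no meaning.

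**The case against.** The strongest reply is that this is an uncontrolled, unpowered registry whose own text already makes it descriptive. Alpha, ordering and p-value labels normally belong in the SAP, which is not shown, and Section 8.10 refers additional methods to it. This stands as far as it goes. The absence of an alpha or a hierarchy is not a fault here, and one cannot say that a descriptive label is missing. But the reply does not remove the contradiction, because Section 8.6.3.2 itself states that a test will be done.

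Several stronger readings are tempting and are not supported:

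- **The Protocol plans 42 tests.** It does not say so. The sex split belongs to the summaries of raw measurements, whereas the zero null makes sense for Z-scores, which have their own paragraph with no sex split. The 42-test figure joins the two.
- **A chance growth finding is more likely than not.** Over between-visit correlations of 0.3 to 0.9 this fails for 14 tests (at most 0.445) and for a false deficit over 42 tests (at most 0.446). For any false positive over 42 tests it holds only below a correlation of about 0.8, where the simulated values are 0.46 to 0.52. Changes within one child share a baseline, so high correlation cannot be set aside.
- **Yearly interims repeat the tests.** Section 8.4.3 describes optional ad hoc summaries and mentions no test or decision.
- **Week 240 height is the only proper primary contrast.** Section 8.2 defines growth by visit, and a Week 240 contrast rests on those who stay to the end. Section 3.3 removes subjects who start new hepatitis C therapy. Which visit matters most is the sponsor's choice.

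**Conclusion.** The point holds as an internal contradiction with a measurable consequence. The Protocol orders a test on a primary safety endpoint that its synopsis excludes, and it leaves visit, measure and scale open.

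If the test is applied to Z-score change at each visit in all subjects, the chance of at least one false positive is about 20% to 45%. If it is also applied in each sex, the chance is about 40% to 75%. Either is well above 5%. These figures assume two-sided 5% per test, true nulls, equal numbers of each sex, a height–weight correlation of 0.5 and between-visit correlation of 0.3 to 0.9. With only one test per measure the chance is at most modest, 9.75% if independent.

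The contradiction needs none of these assumptions. Given the descriptive purpose the matter is of moderate weight, but it concerns the primary endpoint and is easily corrected.

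**What to change.** Reconcile the synopsis, Section 8.6 and Section 8.6.3.2 as follows:

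1. Delete the sentence in Section 8.6.3.2 that orders the signed rank or t-test.
2. In its place, report mean or median change in height and weight Z-score by visit, with 95% confidence intervals and no p-values.
3. Label these results descriptive, at the final analysis and in any interim summary under Section 8.4.3.

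The label is needed as well as the intervals. An interval that excludes zero at one visit is about as likely by chance as a p-value below 5%, so the report should not single out such a visit as a finding.

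If the sponsor keeps a test, limit it to one prespecified Z-score contrast (one measure, one named visit) and amend the synopsis to allow it. One contrast at 5% carries a 5% chance of a false positive. The sponsor should choose the visit and give the reason.

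The cost is wording only, with no change to data collection. The small downside is that no growth result at a single visit or in one sex can be called statistically significant.

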### **8.9. Sample Size**

Due to the observational nature of this study, no formal power or sample size calculations were used.

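### Section 8.6.3.2 plans a test of growth change against zero that contradicts the synopsis; read literally it tests raw height and weight, where zero is the wrong reference for growing children

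*Protocol*

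**What the plan says.** Section 8.2 lists growth first among the primary safety endpoints: "Growth data by visit grouped by age and gender". Section 8.6.3.2 sets out the analysis. Its main paragraph begins "The changes in body height and weight measurements for all subjects will be examined to determine" whether most subjects went up, went down or did not change. It promises summary statistics by sex and overall, then closes with the test. The distribution decides between the signed rank method of Wilcoxon and this alternative: "a one-sample t-test will be done to evaluate if the mean or median change from baseline is different from zero".

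Z-scores are treated separately, further down: "Z-scores for body weight and height and change from baseline in Z-scores for body weight and height will be summarized by visit", with figures of the median and IQR. No test is attached to them there.

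Two other places describe the inferential status of these analyses. The synopsis, under Statistical Methods, states "Statistical hypothesis testing will not be conducted". Section 8.6 states "Analysis of safety measures will be descriptive and will include subjects in the Safety analysis set". Section 8.9 adds that "no formal power or sample size calculations were used".

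**The concern.** There are two problems. The first needs no assumptions: the protocol rules out hypothesis tests in one place and prescribes one in another, on the endpoint that carries the primary objective.

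The second concerns the null value. A child who grows normally gains height and weight, so zero raw change is not the result expected of a safe regimen. A significant increase is the expected finding under normal growth and often also under suppressed growth. Section 1.2 gives concern about treatment effects on growth as a reason for the registry. A reported p-value for an increase in height could be taken as reassurance on exactly that question, although expected growth never enters the comparison. Change in Z-score, which is referenced to age and sex, is the quantity for which zero has the needed meaning.

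**Working it through.** **1. The statements side by side (no arithmetic).**
- Synopsis: no hypothesis testing.
- Section 8.6: safety analysis is descriptive.
- Section 8.6.3.2: a signed rank or t-test of change against zero.

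The third is incompatible with the first, and goes beyond the second, whichever variable is tested.

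**2. Which variable is tested.** The test sentence says only change from baseline. The sentences before it in the same paragraph concern height and weight measurements and changes in them. Z-scores have their own later paragraph, which plans only summaries and figures. The literal reading is therefore raw change, but the protocol does not name the variable.

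**3. What the test would do on the literal reading.** The protocol states no sample size, growth rate, SD or significance level, so there is no figure to reproduce. The inputs below are assumptions, apart from the visit time, which comes from Section 3.2 ("Subsequent study visits will occur at Weeks 24, 48, 72, 96, 144, 192, and 240").

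- Time to Week 24: 24 × 7 / 365.25 = 0.46 year.
- Height gain at 5 cm/year: 5 × 0.46 = 2.30 cm. Halved: 1.15 cm.
- SD of 24-week change: 1.5 to 2.5 cm.
- Two-sided 0.05, one-sample t-test, so power comes from the noncentral t distribution with n − 1 degrees of freedom and noncentrality δ = (mean change / SD) × √n.

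Worked case, halved growth, n=50, SD 2.5: δ = (1.15 / 2.5) × √50 = 3.25; critical value 2.01; rejection probability 0.890.

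| Height, 5 cm/year, Week 24 | Normal growth (+2.30 cm) | Halved growth (+1.15 cm) |
|---|---|---|
| n=20, SD 2.5 | 0.97 | 0.50 |
| n=50, SD 1.5 | >0.999 | 0.9996 |
| n=50, SD 2.5 | >0.999 | 0.890 |
| n=100, SD 2.5 | >0.999 | 0.995 |

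**4. Where rejection is less likely.** Same formula, Week 24, n=50:

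| Case | Normal | Halved |
|---|---|---|
| Height near final, 1 cm/year (+0.46 cm), SD 2 | 0.36 | 0.13 |
| Weight, 3 kg/year (+1.38 kg), SD 4 | 0.67 | 0.22 |

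In these cases the test often fails to reject even under normal growth. Non-significance then reflects small n or little remaining growth; it does not show a shortfall against expected growth.

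**5. The same test on Z-score change, for contrast.** Further assumptions: Week 48, population height SD 6.5 cm, SD of Z-score change 0.3 to 0.5, n=50, and a mean Z-score change of zero under normal growth. With normal growth, rejection is then 0.05 by construction. With growth halved from 3 cm/year, the deficit is 1.5 × 48 / 52.18 / 6.5 = 0.21 Z, and the test rejects with probability 0.84 to above 0.99. With growth halved from 1 cm/year (deficit 0.07 Z), it rejects with probability only 0.17 to 0.37. The Z-score version is therefore not always powerful, but its result refers to expected growth.

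**The case against.** The strongest counter-argument is that Z-score change was meant all along. Section 8.6.3.2 opens by calculating Z-scores by sex and age and speaks of comparing baseline values with the population. It allows a band of negligible change of 0.5 with no unit, and explains the band by the precision of the calculations. Absolute height and weight are then added separately at the end. If Z-score change was intended, zero is a sensible null and the second problem disappears. This stands as a possibility, so it would be too strong to state as fact that raw change is tested. It does not remove the contradiction with the synopsis, and an unnamed variable in the only planned growth test itself needs correcting.

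It is also fair that the practical harm is limited. No decision rule or safety conclusion is tied to the test, and Z-score change is already to be summarised and plotted by visit, so suppressed growth should show there.

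Three stronger readings are tempting but not supported:
- A reader might infer that the test rejects whatever happens to growth. The figures above show that this depends on n, growth rate and SD, none of which the protocol gives. The population also includes adolescents, some already at Tanner Stage 5.
- A reader might count 7 visits × 2 measures × 3 groups = 42 unadjusted tests. The split by sex and overall is attached to the summary statistics, not to the test; without it the count is 7 × 2 = 14.
- A reader might fault the data-dependent choice between t-test and Wilcoxon. That rule is ordinary content for the statistical analysis plan, which is not at hand.

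**Conclusion.** The contradiction between Section 8.6.3.2 and the synopsis, with Section 8.6 alongside, is certain and rests on no assumption. The wrong-reference problem holds on the literal reading, which is the more natural one but is not settled by the text. On that reading, among about 50 or more children growing at 5 cm/year with an SD of 24-week change of 1.5 to 2.5 cm, a halving of growth would still be declared a significant increase with probability 0.89 or more. In smaller groups, near final height or for weight, rejection is less likely and non-rejection is equally uninformative. Because descriptive Z-score output is already planned, what is at stake is a misleading p-value on a primary safety endpoint, not the loss of age- and sex-adjusted information. This should be fixed; it does not undermine the registry.

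**What to change.** Preferred: delete the test of raw height and weight change against zero from Section 8.6.3.2. Report mean and median change from baseline in height Z-score and weight Z-score at each visit with 95% confidence intervals, and keep raw height and weight as descriptive tables. The section then agrees with the synopsis and Section 8.6.

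Alternative, if a test is wanted: state that it applies to change in Z-score, and amend the synopsis and Section 8.6 so that they allow it.

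Either way the cost is protocol and analysis-plan wording, plus a little extra output for the intervals. Z-scores are already to be calculated at baseline and every visit, so no new data are needed.
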